9.2.1 Study time frame

For the main analysis, the study population will comprise all adult OAC naïve (no OAC prescription in the previous 365 days, counted from the date of the first dispensation backward to the end of OAC supply) NVAF patients in Norway dispensed a prescription for an OAC (NOAC or warfarin) for the first time in the study period (cohort 1a), defined as from 1 January 2014 to 30 June 2018 (or later depending on availability of data) and followed until endpoint of interest, the end of the study period or death. Patients will be censored at a switch or a discontinuation.

For exploratory analysis, a second study population (cohort 1b) will comprise all adult NVAF patients in Norway that did not receive an OAC (NOAC or warfarin) in the study period, defined as above.

The look-back period will be at least 5 years from the possible earliest index date of NOACs (1 January 2014) going back to 1 January 2009 (available data cut). The minimum follow-up period will be 1 month and the estimated mean follow-up time will be 18 months.

[figure not shown]

Figure 1: Study design

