9.2.2 Selection criteria

Depending on the data source, the following 2 cohorts will be recruited:

Inclusion criteria

Registry cohort (Cohort 1)

Cohort 1a:

- Age ≥ 18 at the date of first OAC dispensation (index date)
- Diagnosed with atrial fibrillation or flutter in the period 5-year pre-index period. Defined as ICD10 codes; I480 (paroxysmal AF), I481 (persisting AF), I482 (chronic AF), I483 (typical AF), I484 (atypical AF) or I489 (unspecified atrial fibrillation or flutter) as given by either NPR **or** as a OAC (warfarin, dabigatran, rivaroxaban or apixaban) dispensed on the reimbursement code for AF in NorPD (ICD10 I48 or ICPC-2 K78)
- Dispensation of a first-time prescription for an OAC during the study period 1 January 2014 to 31 May 2018. This initiation of an OAC is the index event and requires that there is no previous prescription for any OAC in the preceding 365 days (counted from the date of the first dispensation backward to the end of OAC supply).

Cohort 1b:

- Age ≥ 18 at the beginning of the study period (1 January 2014).
- Diagnosed with atrial fibrillation or flutter prior or during the study period. Defined as ICD10 codes; I480 (paroxysmal AF), I481 (persisting AF), I482 (chronic AF), I483 (typical AF), I484 (atypical AF) or I489 (unspecified atrial fibrillation or flutter) as given by NPR.
- No dispensation of a prescription for an OAC (warfarin, dabigatran, rivaroxaban or apixaban) during the study period 1 January 2014 to 30 June 2018. The index event will be the beginning of the study period (1 January 2014) and requires that there is no previous prescription for an OAC in the preceding 365 days.

EMR cohort (Cohort 2):

- Age ≥ 18 at the date of first OAC dispensation (index date).
- Diagnosed with atrial fibrillation or flutter in the 5-year pre-index period defined as one of the following ICD10 codes in the EMRs obtained from the hospitals in the South-

Eastern Health Region; I480 (paroxysmal AF), I481 (persisting AF), I482 (chronic AF), I483 (typical AF), I484 (atypical AF) or I489 (unspecified atrial fibrillation or flutter).

- Dispensation of a first-time prescription for an OAC (warfarin, dabigatran, rivaroxaban or apixaban) during the study period 1 January 2014 to 31 May 2018. This initiation of an OAC is the index event and requires that there is no previous prescription of any OAC in the preceding 365 days (counted from the date of the first dispensation backward to the end of OAC supply).

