9.2.3 Study population

Cohort 1 sampling:

The NorPD is a pseudonymized register which means that it is not possible to use dispensation of OAC as the starting point and as a source population. Being a pseudonymized register NorPD data needs to be the last register in the data collection that is linked to the other data sources. To circumvent this we will start with the Norwegian Census Register that will identify all Norwegian residents' of the age of 18 years and above during the study period. This dataset is sent to the NPR (for all patients with NVAF and without NVAF plus the relevant co-morbidities). Lastly, NorPD will identify all subjects with at least one OAC dispensation during the study period and link the registers (cohort 1a). A de-identified dataset with all NVAF patients having at least one OAC dispensed in the study period will be delivered to the research group (cohort 1a). Similarly, NorPD will identify all subjects that did not receive an OAC prescription during the study period and link the registers (cohort 1b). A de-identified dataset with all NVAF patients not having received an OAC prescription in the study period will be delivered to the research group (cohort 1b) for exploratory analysis.

[figure not shown]

Figure 2: Cohort 1 sampling procedure flow-chart

Cohort 2 sampling:

From the EMR extraction process all patients diagnosed with NVAf at selected hospitals in Norway between 2009 to the end of study will be selected. This cohort of patients will be linked with NPR and lastly NorPD will be added.

[figure not shown]

Figure 3: Cohort 2 sampling procedure flow-chart

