9.3 Variables

9.3.1 Baseline characteristics

Table 4: Demography and clinical characteristics extracted for cohort 1 and 2

Variable	data source	Definition	Relevance
Age	FRG	Age in year	Co-variate and included in risk scores
Gender	FRG	Male or female	Co-variate and included in risk scores
Origin	FRG	Place of birth categorized as Norway, the Nordic countries, other Europe, rest of the world	Co-variate
Immigration date	FRG	Date of immigration out of Norway	Censoring
Emigration date	FRG	Date of emigration out of Norway	
Date of death	FRG	Date of death	Censoring and outcome variable
Alcoholism	NPR	ICD10 codes: E244, G312, G621, G721, I426, K860, O354, Z714, Z721, E52, K70, T51	Co-variate
Chronic kidney disease (CKD)	NPR	ICD10 code: N18 as an option 1 to define CKD Expanded list of codes to define CKD will be considered as an option 2, This list is being used for another ongoing study and is based on the approaches by Fleet et al (8)., Nielsen et al (9). and Weir et al (10). that in addition to identifying patients from the option 1 will allow an inclusion of patients with cystic kidney disease, unspecified kidney failure, chronic or unspecified nephritic syndrome, nephrotic syndrome, recurrent and	Co-variate

Variable	data source	Definition	Relevance
		persistent hematuria, nephropathy (diabetic, hypertensive, hereditary), chronic tubulo-interstitial nephritis, diabetes mellitus with kidney complications as having renal dysfunction (see Annex 3). The option 2 will be further clarified.	
End stage renal disease	NPR	ICD10 code: N185 or procedure codes KAGD40 (hemodialysis chronic) or KAS (renal transplant)	Co-variate Hemodialysis included in mHASBLED score
Congestive heart failure	NorPD	NorPD reimbursement codes for heart failure: I50 (ICD10) or K77 (ICPC) in ATC code group C	Co-variate. Included in CHA2DS2VASc score
Dementia	NPR	ICD10 codes F00-F04, G30	Co-variate
Diabetes	NorPD	ATC code A10A or A10B	Co-variate
Ischemic stroke	NPR	ICD10 codes: I63	Co-variate
Hemorrhagic stroke	NPR	ICD10: I60-62	Co-variate Included in mHAS-BLED score
TIA	NPR	ICD10 code: G45	Co-variate Included in CHA2DS2VASc score
Stroke&tia	NPR	ICD10: I60-I64	Co-variate Included in CHA2DS2VASc score
Thromboembolism	NPR	ICD10: I74	Co-variate

Variable	data source	Definition	Relevance
			Included in CHA2DS2VASc score
Hypertension	NorPD	Reimbursement codes in NorPD in ATC code group C: E10-E13, E15 (ICD10) or K86, K87 (ICPC)	Co-variate Included in mHASBLED and CHA2DS2VASc risk score

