9.6 Data management

There will be 3 main steps;

- Merge together all data and build the analytical dataset
- Create patient cohorts
- Populate tables and figures

Statistical Analysis System (SAS software, version 9.4, SAS Institute, Cary, NC) will be used to all data handling to prepare analytical dataset.

The data from NorPD and NPR are considered high quality register data, however, some quality checking and data cleaning will be done to check for reasonability and consistency of data, e.g. by cross-tabulation of patient characteristics compared to publically available data sources and so forth. From these initial cut of data, further programming will be applied to identify the eligible patient cohorts with additional information of interest to address study objectives as include the following:

- All data from different sources will be retrieved/imported into SAS.
- Completeness of data regarding the number of variables and observations will be verified against the source.
- Quality control of the reasonability and consistency of information and data cleaning will be done
- Datasets will be merged to provide all information needed from various sources to define the patient cohorts.
- Patient cohorts will be defined and include all subjects which fulfills the cohort's inclusion criteria (section 9.2.2).
- Co-morbid conditions of interest within five years prior to index date will be identified, and various co-morbidity scores will be calculated (section 9.3.1).
- Concomitant medications at baseline and during the follow-up according to the ATC codes as described in section 9.3.1 will be selected.

- Adherence to each OAC will be estimated as described in section 9.3.3.
- All outcomes of interest (new events during follow-up) will be selected according to sections 8.1-3 and 9.3.4.1-2.
- Three different subset of cohorts for survival analysis based on exposure to OAC (continuous use or switched) will be defined as described in section 9.3.2.
- Finally a clean ready-to-use analysis database will be constructed, which will contain complete set of all data including the derived variables, according to the study protocol.
- Tables and figures will be populated

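### No minimum residence in Norway before index is required, so recent immigrants count as OAC-naive by default and may carry a truncated history; the effect is probably very small and the remedy is cheap

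*Protocol*

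**What the plan says.** - **Sampling.** Section 9.2.3 starts from the census register, which will "identify all Norwegian residents' of the age of 18 years and above during the study period". Residence at some time in the study period is enough.
- **Naive status.** Section 9.2.2 requires "no previous prescription for any OAC in the preceding 365 days", counted back from the first dispensation to the end of OAC supply. Section 9.3.2 works out that supply from dispensations.
- **AF.** Cohort 1a needs "Diagnosed with atrial fibrillation or flutter in the period 5-year pre-index period" in the patient register, or an OAC dispensed on the AF reimbursement code.
- **History.** Section 9.6 states: "Co-morbid conditions of interest within five years prior to index date will be identified".
- **Migration dates.** Table 4 in section 9.3.1 defines immigration date as "Date of immigration out of Norway", with censoring as its relevance. The emigration row below it has no relevance entry in the text as extracted. Section 9.3.3 lets migration end the adherence period. The outcome follow-up rules in 9.2, 9.2.1 and 9.7.1 do not mention it.
- **Residence.** None of the criteria for cohorts 1a, 1b and 2, nor the shared exclusions, sets a minimum period of residence before index.

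**The concern.** Naive status and freedom from earlier disease are both inferred from the absence of a Norwegian record. That inference needs the person to have been in Norway, and so visible to the registers, during the window. For a recent arrival the record is empty whatever the true history.

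Three things depend on it. The primary objective is a comparison among OAC-naive starters, and a patient already anticoagulated abroad could enter as a new user. Medical history feeds the propensity score and the risk scores, so an unrecorded earlier stroke makes a patient look lower-risk when matched. The valvular AF and venous thromboembolism exclusions also rely on register codes and can be missed. Place of birth is a covariate, but it does not measure time since arrival and does not identify Norwegian-born people who have returned.

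**Working it through.** The protocol gives no figure on this point, so the first step is a comparison of passages. The arithmetic after it is for scale only.

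**1. What each rule needs, and what is visible**

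| Rule | Window | Arrived under about 1 year before index | Arrived 1 to 5 years before index |
|---|---|---|---|
| OAC-naive (9.2.2) | 365 days | Passed by default for the time abroad | Testable, except where supply brought from abroad ran into the window |
| Comorbidity history (9.6) | 5 years | Mostly unobserved | Partly observed |
| One-year score items (Table 4: hypertension, recent stroke, recent major bleeding, NSAID or antiplatelet use, diabetes) | 1 year | Partly observed | Fully observed |
| Prior stroke/TIA, peripheral artery disease, renal and liver codes | Up to 5 years | Truncated | Truncated |
| Age and sex points | None | Unaffected | Unaffected |

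No rule uses the immigration date to separate these columns.

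**2. Number of patients**

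Input from section 9.5: about 70,000 naive patients. The shares of recent arrivals are assumptions.

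- Under 1 year of residence, assumed 0.1 to 0.5%: 70,000 × 0.001 = 70; 70,000 × 0.005 = 350.
- Under 5 years, assumed 0.5 to 2%: 70,000 × 0.005 = 350; 70,000 × 0.02 = 1,400.
- Extreme, assumed 3%: 70,000 × 0.03 = 2,100.

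**3. Possible shift in a rate ratio**

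Let f be the share of misclassified patients in an arm and R their risk relative to the other patients. The crude bias factor is

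(1 + f_NOAC × (R − 1)) / (1 + f_warfarin × (R − 1)).

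All values of f and R are assumptions.

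- f equal in both arms (1% and 1%), R = 2: 1.01 / 1.01 = 1.000.
- 1% against 2%, R = 2: 1.01 / 1.02 = 0.990.
- 0% against 3%, R = 2: 1 / 1.03 = 0.971.
- 0% against 3%, R = 3: 1 / 1.06 = 0.943.

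**4. Against the protocol's own precision**

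The matched dabigatran size reproduces: 70,000 × 0.11 × 0.90 = 6,930. At a relative risk of 1.00 and a stroke proportion of 2.43%, SE(log RR) = √(2 × (1 − 0.0243) / (0.0243 × 6,930)) = 0.108. The interval is exp(±1.96 × SE) = 0.810 to 1.235, in line with 0.81 to 1.24 in Table 8. A factor of 0.971 is small beside that width.

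**The case against.** The strongest reply is that this hardly matters. Section 7 calls the Norwegian population stable, nothing in the documents suggests that recent arrivals favour one drug, and place of birth is already a covariate and partly balances them. That stands, and it keeps the point at the lowest severity.

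The documents also do not support four stronger readings that a reader might infer.

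- *That section 9.2.1 is contradicted.* It says "The look-back period will be at least 5 years from the possible earliest index date of NOACs" and then gives the available data cut. This describes the calendar coverage of the data and does not promise five observable years for each patient.
- *That migration dates are kept only for censoring.* The abstract lists migration status among the demographics and section 9.4 lists both dates as key variables, without limiting their use. The censoring entry may be a cell merged across the immigration and emigration rows. What can be said is that no stated rule uses the immigration date for eligibility.
- *That recent arrivals enter as free of disease.* AF must still be recorded in Norway, and section 9.4 retrieves all codes for each admission, so chronic conditions coded at the AF contact are captured. Several score items look back one year only.
- *That everyone with untestable naive status is a prevalent user.* Only those already anticoagulated abroad are; the 70 to 350 is an upper bound under its assumed shares.

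Deferring the matter to the SAP is not a full answer, because the eligibility criteria are fixed in the protocol.

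**Conclusion.** The gap is real and minor. As written, the plan classes arrivals within about a year before index as OAC-naive without being able to test it, and it can truncate the history of arrivals within five years. The documents do not give the number; the assumed shares put it at 70 to 350 and 350 to 1,400 of 70,000. The effect on the rate ratios is probably very small: none if the arms are equally affected, and a factor of 0.971 with 0% against 3% affected and doubled risk. The shares and relative risks are assumptions, and the factor is crude and ignores matching. The wording of the immigration row in Table 4 is an error whatever the size of the effect.

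**What to change.** 1. In section 9.2.2, for cohorts 1a, 1b and 2, add continuous registered residence in Norway (census register) for at least 365 days before index. For cohort 1b, whose index is 1 January 2014, this means residence since 1 January 2013.
2. Add a sensitivity analysis restricted to patients with five years of continuous residence, because the 365-day rule leaves truncated five-year histories in the main analysis.
3. In Table 4, define immigration date as the date of immigration into Norway and give it an eligibility and look-back role. Keep emigration date for censoring.
4. Name emigration in the outcome follow-up rules of 9.2, 9.2.1 and 9.7.1, in line with the adherence rule in 9.3.3.

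The dates are already requested, so no new data are needed. The cost is one inclusion line, one sensitivity analysis, small text edits and a very small loss of patients.

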Peripheral artery disease	NPR	ICD10: I739	Co-variate Included in CHA2DS2VASc score
Ischemic heart disease	NPR	ICD10: I20-I25	Co-variate
Myocardial infarction	NPR	ICD10: I21-I22	Co-variate
Angina pectoris	NPR	ICD10: I20	Co-variate
Chronic obstructive pulmonary disease	NorPD	Reimbursement codes: J44 (ICD10) or R95 (ICPC) in ATC group R03	Co-variate
Cancer	NPR	ICD10 codes: C00 to C97	Co-variate Included in Charlson Co-morbidity score
Leukemia	NPR	ICD10 codes: C90-C96	Co-variate Included in Charlson Co-morbidity score
Lymphoma	NPR	ICD10 codes: C80 to C88	Co-variate Included in Charlson Co-morbidity score
AIDS	NPR	ICD10 codes B20 to B24	Co-variate

Variable	data source	Definition	Relevance
			Included in Charlson Co-morbidity score
Thrombocytopenia	NPR	ICD10 codes: D692, D693, D694, D695, D696, D698, D699	Co-variate
Anemia	NPR	ICD10 codes: D65-D67, D680, D681, D682, D683, D684, D685, D686, D688, D689, D50-D53, D55-D59, D60-D64	Co-variate
Hypo/hyperthyroidism	NPR	ICD10 code: E03 / E05	Co-variate
Systemic connective tissue disease	NPR	ICD10 codes: M30 to M36	Co-variate Included in Charlson Co-morbidity score
Peptic ulcer and bleeding	NPR	ICD10 codes: Ulcer K25 to K29. Gastrointestinal bleeding K920/K921/K922	Co-variate Included in Charlson Co-morbidity score
Chronic liver disease and impairment	NPR	ICD10 codes: K70-K77	Co-variate Included in mHASBLED score
Renal impairment	NPR	ICD10 codes: D63.8, E10.2, E11.2, E13.2, I12.0, I13.1, I13.2, N02.x, N03.x, N04.x, N05.x, N07.x, N08.x, N11.x, N14.x, N18.x, N19, Q61.x	Co-variate Used in stratified analyses
Surgery performed in the study period	NPR	All NCSP codes including codes for active surgery	Co-variate. Adjust or exclude for in bleeding outcomes
Imidazol and triazol derivates	NorPD	ATC codes J02AB and J02AC	Co-variate. Interaction

Variable	data source	Definition	Relevance
Low-dose aspirin	NorPD	ATC code: B01A C06	Co-variate Included in mHASBLED score
Immunosuppressive treatments	NorPD	ATC code: L04A	Co-variate
Anti-platelet treatment (non aspirin)	NorPD	ATC code: B01A	Co-variate Included in mHASBLED score
Non-steroidal anti-inflammatory drugs (NSAID)	NorPD	ATC code: M01A	Co-variate. Included in mHASBLED score
Acid secretory drugs	NorPD	ATC code: A02B	Co-variate
Heparin	NorPD	ATC code: B01AB	Co-variate
Anti-arrytmic drugs class iii	NorPD	ATC code C01BD	Co-variate. Interaction
Rifampicin	NorPD	ATC code J04AB	Co-variate. Interaction
Anti-hypertensives	NorPD	ATC code: C02	Co-variate

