Diuretics	NorPD	ATC code: C03	Co-variate
Beta-blockers	NorPD	ATC-code: C07	Co-variate
Calcium antagonists	NorPD	ATC-code: C08	Co-variate
Renin-angiotensin system drugs	NorPD	ATC-code: C09	Co-variate

Variable	data source	Definition	Relevance
Lipid-modifying drugs	NorPD	ATC-code: C10	Co-variate
Reduced or standard dose NOAC at index	NorPC	Indicator variable whether on reduced (15 mg riva, 2,5 mg api, 110 mg dabi) or standard (20 mg riva, 5 mg api, 150mg dabi) at index dispensation	Co-variate
Prior OAC use	NorPD	Previous OAC use. OAC availability (time of exhaustion of last dispensation) in 365 days prior to index dispensation. From the time of exhaustion of last dispensation and initiation of OAC in study period (> 12 months pre-index)	Co-variate
Previous bleeding hospitalization	NPR	ICD codes listed in section 9.3.4.2	Co-variate Included in mHASBLED
Modified HAS-BLED score	NPR and NorPD	
 - Hypertension defined by dispensation of at least one anti-hypertensive drug (see definition for hypertension above) last year prior to index date. 1 point - Renal impairment as defined by either hemodialysis (procedure code KAGD40) or kidney transplantation (procedure code KAS) or CKD stage 3 and 4 (ICD10 code N183, N184, N185). Expanded list of codes to define CKD will be considered as an option 2, 1 point - Liver impairment (ICD10 K70-K77). 1 point - Stroke during the last year prior to index visit (see definition). 1 point - Prior major bleeding (critical organ) last year before index date (see definition in 9.3.4.2) 1 point 	Bleeding risk score used as co-variate and effect modifier

Variable	data source	Definition	Relevance
		
 - Age \geq 65 years. 1 point - Therapy with either Nonsteroidal Anti-inflammatory Drugs (NSAID M01A) or anti-platelets (B01AC) in the previous year before index date. 1 point - Alcoholism (as defined by ICD10 codes above). 1 point 
Total HAS-BLED score from 0 to 8
	

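### The Alcoholism code list omits F10, so patients coded only for alcohol dependence count as not alcoholic and lose a HAS-BLED point; a lesser fault is that the Anemia list includes coagulation defects

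*Protocol*

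**What the plan says.** Table 4 in protocol section 9.3.1 applies to cohorts 1 and 2. It takes Alcoholism from the Norwegian Patient Register (NPR) and defines it by the ICD-10 codes "E244, G312, G621, G721, I426, K860, O354, Z714, Z721, E52, K70, T51". The row is marked as a covariate.

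The modified HAS-BLED row of the same table reuses that list: "Alcoholism (as defined by ICD10 codes above). 1 point". The score is described as "Bleeding risk score used as co-variate and effect modifier", with "Total HAS-BLED score from 0 to 8".

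The Anemia row, also from NPR and also a covariate, reads "ICD10 codes: D65-D67, D680, D681, D682, D683, D684, D685, D686, D688, D689, D50-D53, D55-D59, D60-D64".

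Table 5 adds a free-text search for alcohol abuse in the electronic medical records (EMR), for cohort 2 only. Section 9.7 bases the propensity scores on demographic variables, medical history, comorbidities and concomitant medication, and leaves the detailed modelling to the SAP.

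**The concern.** A variable called Alcoholism should find patients whose hospital record carries a diagnosis of alcohol dependence. In ICD-10, the coding system the protocol adopts for NPR (section 9.4), that diagnosis sits in F10. Without F10, the rule finds such a patient only if a second, listed code is also present.

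The gap enters in two places: the covariate itself, and one of the eight HAS-BLED points. Intracranial haemorrhage is a primary outcome, and the protocol's own score treats alcoholism as a bleeding risk factor. If alcohol abuse also differs between patients started on warfarin and those started on a NOAC, the missed patients leave some confounding in that comparison.

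The Anemia row raises a smaller issue of the same kind: one indicator pools anaemia with disorders of coagulation.

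**Working it through.** The protocol states no figure for this point, so the check is an entry-by-entry comparison of the lists with the ICD-10 blocks, followed by an illustration of size.

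**Alcoholism list (12 entries)**
- Seven are organ or system disease due to alcohol: E244, G312, G621, G721, I426, K860, K70.
- Five are other items: O354 (fetal damage from alcohol), Z714 (counselling), Z721 (alcohol use), E52 (pellagra), T51 (toxic effect).
- 7 + 5 = 12. None is F10, and none is from the F chapter.

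**Data limit or stated choice?** Neither. The Dementia row of the same table takes F-chapter codes from NPR: "ICD10 codes F00-F04, G30". No section gives a reason for leaving F10 out. The chronic kidney disease row says that its expanded list is still to be clarified; the Alcoholism row has no such reservation.

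**Effect of the rule as written.** For a patient coded F10 and no other listed alcohol code:
- Alcoholism covariate = 0.
- HAS-BLED alcohol component = 0 where 1 is intended, so the total is one point too low. The eight components carry one point each, which agrees with the stated maximum of 8.

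**Other alcohol information.** In cohort 1 there is no other direct indicator. Cohort 2 has the EMR free-text search, but section 9.2 makes that cohort conditional on access being granted, and section 9.7 analyses the two cohorts separately.

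**Anemia list**
- Anaemia codes: D50-D53, D55-D59 and D60-D64.
- Coagulation defects: D65, D66 and D67 (3 codes) plus D680 to D686, D688 and D689 (9 codes), 12 in all.
- D685 and D686 are thrombophilias, so the indicator mixes anaemic, bleeding-prone and clot-prone patients. Table 4 has no separate coagulation-defect covariate; the nearest row is Thrombocytopenia, which uses D69 codes.

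**Illustration of size (assumptions, not protocol figures).** Let p1 and p0 be the shares of F10-only patients in the two arms and R the relative risk of intracranial haemorrhage from alcohol abuse. If these patients are wholly unadjusted, the ratio is multiplied by

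B = [1 + p1(R − 1)] / [1 + p0(R − 1)].

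| p1 | p0 | R | B | Arms reversed |
|---|---|---|---|---|
| 3% | 2% | 2 | 1.03/1.02 = 1.010 | 0.990 |
| 3% | 2% | 2.5 | 1.045/1.03 = 1.015 | 0.986 |
| 5% | 3% | 3 | 1.10/1.06 = 1.038 | 0.964 |
| 5% | 2% | 3 | 1.10/1.04 = 1.058 | 0.945 |

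At a relative risk of 1.00, protocol Table 10 gives planned intervals of 0.74 to 1.35 (dabigatran), 0.79 to 1.27 (apixaban) and 0.80 to 1.26 (rivaroxaban). Against the narrowest, on the log scale, the bias is ln(1.010)/ln(1.26) = 0.010/0.231 ≈ 4% to ln(1.058)/ln(1.26) = 0.056/0.231 ≈ 24% of the distance from 1.00 to the upper limit.

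**The case against.** The strongest reply concerns consequence rather than fact.

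- **No prevalence is given.** The protocol does not say how many patients carry F10, or F10 alone. A reader might infer that the indicator misses most patients with alcohol problems. Nothing in the document supports a figure for that. This part of the objection stands.
- **Correlated covariates help.** A reader might infer that the propensity score leaves every missed patient unbalanced on alcohol. That goes too far. Table 4 also lists liver disease, peptic ulcer and gastrointestinal bleeding, previous bleeding hospitalisation and the Charlson index. If these enter the score, they would recover part of any imbalance. The list is the only direct alcohol indicator in cohort 1, not the only source of adjustment. This stands too.
- **K70 under both liver and alcohol.** A reader might call this double counting, because one code yields two points. The score defines liver impairment and alcoholism as separate components, and a patient with alcoholic liver disease has both. No stated rule is broken.
- **Anaemia.** This variable enters none of HAS-BLED, CHA2DS2-VASc or Charlson, and the coagulation defects are still captured, only pooled. A reader might infer a biased estimate, but the documents show none.
- **Residual confounding and later repair.** Section 9.9 concedes residual confounding in general, and section 9.7 lets the SAP modify the plan. The concession does not name this gap. The option to repair limits the harm but does not make the list right: the codes are fixed in the protocol and reused by reference in the score.

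**Conclusion.** The Alcoholism definition is wrong as written and should be corrected. It omits the ICD-10 category for harmful use, dependence and withdrawal, and it carries the omission into the modified HAS-BLED score. F10-only patients are classed as not alcoholic and score one point too low. In cohort 1 no other direct alcohol indicator can catch them.

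The resulting bias in the intracranial haemorrhage comparison cannot be computed from the protocol and is probably modest. The 1% to 6% illustration rests on assumed prevalences of 2% to 5%, an assumed relative risk of 2 to 3, and no recovery through other covariates. Its direction is unknown. It does not undermine the primary analysis, but it is an avoidable error.

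The Anemia list is a lesser fault of labelling and granularity, with no demonstrated effect on an estimate. The meanings of the codes come from ICD-10 itself, which the protocol adopts.

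**What to change.** 1. Add F10, all subcodes, to the Alcoholism row of Table 4. The HAS-BLED component follows automatically, because it refers back to that row.
2. Name F10 in the NPR data request. Section 9.2.3 speaks of relevant comorbidities, while section 9.4 plans to retrieve ICD-10 diagnoses with primary and subsequent codes, so it is not certain that F10 would be delivered if the request follows Table 4.
3. Restrict Anemia to the D50-D64 codes already listed. Make D65-D68 a separate coagulation-defect covariate, with thrombophilia (D685, D686) distinguished.

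The cost is an edit to two code-list rows, one new row and a check of the data request. Under section 9.7, only major changes to the primary endpoint definitions or their analyses call for a protocol amendment, so the covariate changes could also be made in the SAP. It is cheapest before extraction, because the registry holders perform the linkage and a later repair could need a second request.
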